## 8 STUDY VARIABLES AND METHODS OF ASSESSMENT

### 8.1 Study Subjects

#### 8.1.1 Demographic Data and Baseline Characteristics

The following demographic data and baseline characteristics will be documented at Screening:

- Age
- Sex
- Race and ethnicity
- Body weight
- Height
- Smoking status
- Prior HS-related surgeries (i.e., if prior surgeries have been performed and number and type of prior surgeries). Subjects with prior HS-related surgery will be identified during a medical review before database lock

#### 8.1.2 Medical and Surgical History

A complete medical history (including non-HS-related surgical history), with details of tobacco and alcohol use, will be obtained from each subject at Screening. The medical history will be reviewed and updated on Day 1 to ensure that the subject remains qualified for the study.

#### 8.1.3 Hidradenitis Suppurativa Medical and Surgical History

The diagnosis of HS is based on the following criteria, set by the 2nd Conference of the HS Foundation in San Francisco [13]:

- Disease onset after puberty
- Involvement of at least 2 areas of skin rich in apocrine glands
- History of recurrent drainage of pus from the affected areas

The HS medical history will be documented in terms of:

- Duration of HS (years)
- Family history of HS

- 
- Allocation of affected areas to the Hurley Stage gradation of disease severity [13]. Subjects with Hurley Stage II and III, indicating moderate and severe HS, will be enrolled into the study (Appendix 17.1)

All surgical interventions for HS before Screening will be documented in the eCRF

### 8.1.4 Prior and Concomitant Therapy

All prior therapy taken during the 3 months before Screening and all concomitant therapy will be documented. For details, refer to Section 5.8.

## 8.2 Efficacy Variables

### 8.2.1 Overview of Variables

Efficacy will be assessed on the basis of the following variables:

- HS clinical parameters
- HiSCR, based on HS clinical parameters
- HS-PGA, based on HS clinical parameters
- Modified Sartorius Score (mSS), based on HS clinical parameters
- Lesions, based on HS clinical parameters
- Erythema assessment
- Patient's Assessment of Drainage
- Use of analgesic therapy
- Patient's Global Assessment of Skin Pain (NRS)
- DLQI
- HADS
- SF-36v2
- EQ-5D-5L
- Photographic documentation of affected areas

### 8.2.2 Methods of Assessment

#### 8.2.2.1 Hidradenitis Suppurativa Clinical Parameters

To evaluate the severity of illness, the following HS clinical parameters will be assessed and documented at Screening, at Week 0 (Day 1), and at prespecified times during the study, as outlined in the [Schedules of Assessments](#) through Week 44 or an early discontinuation visit and the 3-month Post-Treatment Follow-Up visit, if the subject discontinues before Week 44:

- Affected area (i.e., left and right axilla, left and right sub/inframammary area, intermammary area, left and right buttock, left and right inguino-crural fold, perianal, perineal area, other [to be specified]), as described in guidance provided to the investigator

NOTE: lesions in each affected area will be counted. The identification of lesions will be performed according to standard definitions of elementary cutaneous lesions.

- 
- Number and type of lesions (i.e., abscesses, inflammatory nodules, non-inflammatory nodules, non-draining fistulas, draining fistulas, hypertrophic scars, other lesions [folliculitis, pustules])
  - Longest distance between 2 relevant lesions (mm)
  - Are lesions clearly separated by normal skin? (yes/no)

### **8.2.2.2 Hidradenitis Suppurativa Clinical Response (HiSCR)**

The HiSCR is defined by the status of 3 types of lesions [20]:

- Abscesses
- Inflammatory nodules
- Draining fistulas

The definition for response to treatment based on HiSCR relative to Day 1 is:

- At least 50% reduction in AN count
- No increase in number of abscesses
- No increase in number of draining fistulas

A subject is considered to be a HiSCR responder only if all 3 criteria above are fulfilled. If any 1 of the 3 criteria is missing, the HiSCR response will be recorded as missing. Additionally, the HiSCR25 response will be calculated. The definition of a HiSCR25 responder relative to Day 1 is:

- An at least 25% reduction in AN count
- No increase in number of abscesses
- No increase in number of draining fistulas

A subject is considered to be a HiSCR25 responder only if all 3 criteria above are fulfilled.

The HiSCR will be assessed at each of the prespecified times when the HS clinical parameters are scheduled to be assessed during the study after Day 1, as outlined in the [Schedules of Assessments](#). The score will be calculated using data recorded for HS clinical parameters in the eCRF (Section [8.2.2.1](#)).

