## 7.2 Main Period (16 Weeks)

The following section describes all study assessments and procedures that have to be performed in the Main Period (double-blind). For each cohort, the Main Period starts at Week 0 (Day 1, immediately before first administration of IMP) and consists of a 2-week Induction Phase (ends immediately after administration of IMP at Week 2) followed by a 14-week Maintenance Phase through Week 16 (ends immediately after administration of IMP at Week 16). An overview of the visit schedule is available in the [Schedule of Assessments - Screening and Main Period \(All Subjects\)](#).

Before administration of IMP, the following assessments and procedures will be performed at the visits to the study site, as indicated:

- Review all relevant inclusion and exclusion criteria (see Section [4.1](#) and [4.2](#)) to confirm eligibility for participation in the study (*Week 0 [Day 1]*)
- Review and record concomitant therapy, as specified in the exclusion criteria (Section [4.2](#)), to confirm eligibility for participation in the study (*Week 0 [Day 1]*)

- 
- Urine pregnancy test, required for all women of childbearing potential (*Weeks 0 [Day 1], 4 [France only], 8 [France only], 12 [France only], 16*)
  - Blood sample for analysis of safety laboratory parameters (*Weeks 4, 8 [France only], 12 [France only], 16*)
  - Review medical and surgical history to confirm eligibility for participation in the study (*Week 0 [Day 1]*)
  - HS medical and surgical history (*Week 0 [Day 1]*)
  - Physical examination (*Weeks 0 [Day 1], 16*)
  - ECG (*Week 16*)
  - Vital signs (*Weeks 0 [Days 1 and 4], 1, 2, 4, 6, 8, 10, 12, 14, 16*)
  - HS clinical parameters (*Weeks 0 [Day 1], 2, 4, 6, 8, 10, 12, 14, 16*)
  - Erythema assessment (*Weeks 0 [Day 1], 2, 4, 6, 8, 10, 12, 14, 16*)
  - Continue documentation of patient-reported outcomes:
    - Patient's Global Assessment of Skin Pain (NRS) (*daily in e-diary throughout Main Period*)
    - Analgesic therapy (*daily in e-diary throughout Main Period*)
    - Patient's Assessment of Drainage (*daily in e-diary throughout Main Period*)
    - DLQI (*Weeks 0 [Day 1], 16*)
    - HADS (*Weeks 0 [Day 1], 16*)
    - SF-36v2 (*Weeks 0 [Day 1], 16*)
    - EQ-5D-5L (*Week 0 [Day 1], 16*)
  - Citrate plasma sample for analysis of:
    - IFX-1 (*Weeks 0 [Day 4], 1, 2, 4, 6, 8, 10, 12, 14, 16*)
  - Plasma sample for analysis of:
    - C3a (*Weeks 0 [Day 1], 2, 16*)
    - C5a (*Weeks 0 [Days 1 and 4], 2, 6, 16*)

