The estimated dose-response curve will be used to estimate the MED and  $ED_{50}$ . The MED is defined as the minimum dose, at which the HiSCR at Week 16 is at least 15% higher than the HiSCR at Week 16 in the placebo group. An improvement of 15% over placebo in HiSCR at Week 16 is considered as clinically relevant [15]. The  $ED_{50}$  is defined as the minimum dose that achieves 50% of the maximum achievable effect over placebo. Standard formulas for the estimation of  $ED_{50}$  will be used and will be explicitly stated in the statistical analysis plan.

Multiple imputations will be performed for subjects with missing data on HiSCR at Week 16 who did not discontinue before Week 16 because of one of the following reasons:

- Disease relapse
- Progressive disease
- Lack of efficacy

Subjects who discontinued before Week 16 because of one of the above mentioned reasons will be treated as not having achieved HiSCR at Week 16. All further specifications for multiple imputations are based on the assumption that the number of subjects that need to have the HiSCR at Week 16 imputed, will be relatively small.

Multiple imputations will be performed based on the assumption that HiSCR response at Week 16 is missing at random, i.e. missingness will not depend on the HiSCR at Week 16 itself but will only depend on the factors in the imputation model. The factors that will be used in the multiple imputation model for HiSCR at Week 16 are HiSCR at prior visits, cohort, baseline Hurley Stage, baseline AN count, and concomitant use of antibiotics. We anticipate that baseline Hurley Stage, baseline AN count and concomitant use of antibiotics will not be

---

missing for subjects in the intent-to-treat population. The multiple imputation model will be using fully conditional specification logistic regression. We will perform 20 imputations using a random seed of 122007 using SAS PROC MI.

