The MCP-Mod approach as outlined above will be applied to all 20 imputed datasets. If the MCP step results in a non-significant dose-response signal for more than one of the 20 datasets, the results will be considered as not robust enough for dose-response estimation. In this case, the Mod step will not be performed. For the estimation of the dose-response curve for each candidate model (Mod step), the individual model parameters ( $ED_{50}$  for the  $E_{max}$  model and  $ED_{50}$  and  $\delta$  for the logistic model) from the analysis on each imputed dataset will be combined using Rubin's rule.

The percentage of subjects with a response on the basis of the HiSCR (Section 8.2.2.2) determined at Week 12 before administration of IMP will be analyzed in the same way as the primary endpoint.

For all other continuous efficacy endpoints, the absolute values and changes from baseline (absolute and relative) will be summarized by display of basic descriptive statistics (e.g., number of observations (n), mean, standard deviation, minimum, median, maximum, lower quartile, upper quartile, and upper and lower boundary of the 95% CI for the mean) by time point.

Model-based analyses (e.g. analysis of covariance [ANCOVA], Poisson, and logistic regression models) for continuous, count, and binary endpoints will be defined in the statistical analysis plan as deemed necessary and possible.

All categorical efficacy endpoints will be summarized by time point using absolute and relative frequencies including 95% exact CIs based on the binomial distribution.

Sensitivity analyses will be defined for all efficacy endpoints if deemed necessary.

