## **10.10 Handling of Missing Data**

Data imputation rules are defined for missing values for the primary efficacy endpoint of percentage of subjects with a response, as measured by HiSCR at Week 16. Subjects with missing baseline assessments (baseline assessments might be obtained at Screening or at Day 1 before first infusion of IMP) necessary for the calculation of the HiSCR at Week 16 will not be randomized (i.e., there shall be no missing baseline values for HiSCR). Missing values for assessments at Week 16 necessary for the calculation of HiSCR at Week 16 will be replaced by multiple imputation, as described in section [10.5.1](#).

All other missing data will not be replaced.

Sensitivity analyses will be conducted based on the PPS. Further sensitivity analyses (e.g., evaluating patients with missing HiSCR at Week 16 as non-responders) will be defined in the statistical analysis plan if deemed necessary.

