## 12 DOCUMENTATION

### 12.1 Electronic Case Report Forms

All data beside ePRO required by this clinical study protocol will be collected in an eCRF and entered into a database validated by the CRO for eCRFs.

The sponsor or its designee will supply the study site with eCRFs. The sponsor or its designee will make arrangements to train appropriate study site personnel in the use of the eCRF.

These eCRFs are used to transmit information collected on the performance of this study to the sponsor and regulatory authorities. eCRFs must be completed in English.

Data entered in the eCRF will be stored in a centralized database on a remote server. Data will be entered by study site personnel who can access the system through a personal user identification and password assigned by the system administrator.

Data will be entered directly into the eCRF via a single data entry process. In the eCRF, subjects will be identified by their subject numbers. The eCRF is to be dated and signed by the investigator or a qualified person who has been delegated by the investigator to do so on his/her behalf, as documented on a signature delegation log filed in the investigator site file.

After completion of the entry process, computer logic checks will be run to identify items, such as inconsistent dates, missing data and questionable values. Queries may be issued by sponsor personnel (or designees) and will be answered by the site.

Corrections to the eCRF database are recorded in an audit trail that captures a complete record of all information. The new information, identification of the person making the correction, the date the correction was made, and the reason for change are captured in a new record.

---

The principal investigator must review the eCRFs for completeness and accuracy and must sign and date the appropriate eCRFs as indicated. Furthermore, the principal investigator must retain full responsibility for the accuracy and authenticity of all data entered into the eCRFs.

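### A missing HiSCR criterion overrides an observed failure, so a known Week 16 non-responder can be imputed as a responder; a minor correction with very small expected effect

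*Combined protocol and SAP*

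**What the plan says.** Section 8.2.2.2 defines response strictly: "A subject is considered to be a HiSCR responder only if all 3 criteria above are fulfilled". It then adds: "If any 1 of the 3 criteria is missing, the HiSCR response will be recorded as missing". There is no exception for a subject whose available criteria already include a failure.

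Section 10.5.1 imputes HiSCR itself, as a binary variable, by logistic regression: "The factors that will be used in the multiple imputation model for HiSCR at Week 16 are HiSCR at prior visits, cohort", followed by baseline Hurley Stage, baseline AN count and antibiotic use. No Week 16 lesion count or criterion is in the list. The only override to non-response is discontinuation for relapse, progression or lack of efficacy.

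Section 10.10 is worded differently: "Missing values for assessments at Week 16 necessary for the calculation of HiSCR at Week 16 will be replaced by multiple imputation". That could suggest imputing the counts, but it refers back to 10.5.1 for the method. Its analysis of missing values as non-response is an example, to be used if judged necessary.

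Two further rules depend on this derivation. Section 10.5.1 skips the Mod step on this condition: "If the MCP step results in a non-significant dose-response signal for more than one of the 20 datasets". It also extends the method to the Week 12 endpoint, which is "determined at Week 12 before administration of IMP will be analyzed in the same way as the primary endpoint".

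**The concern.** The derivation discards information that fixes the outcome. Suppose a subject's AN count has not fallen by half at Week 16 and the draining-fistula count is blank. That subject is a non-responder whatever the blank value is. Under the written rule the subject becomes missing and is drawn as a responder in some of the 20 datasets. The exploratory component tables in section 10.4.1 could show the same subject failing the AN criterion.

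There is a matching error in the other direction. A subject who meets every available criterion is very likely a responder, but is imputed from a model that cannot see this.

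At stake are avoidable noise in the primary endpoint, a slightly lower chance of passing the 19-of-20 rule and, if missingness depends on lesion status, a small bias.

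**Working it through.** **Inputs from the protocol.** Section 10.2: response rates 25, 30, 45, 55 and 60%; cumulative doses 0, 2000, 4800, 8000 and 10,800 mg; Emax ED50 3000; logistic ED50 3500 and delta 1100; one-sided alpha 0.025; 35 per cohort (175 in total) to leave at least 29. Section 7.2: seven HiSCR assessments before Week 16 (Weeks 2, 4, 6, 8, 10, 12 and 14).

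**Assumptions.** The protocol gives no rate of partial missingness; 1-2% of subjects is assumed. The share q of non-responders who visibly fail an available criterion is assumed to be 0.60-0.95.

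**Step 1: the plan's own figure.** With optimal contrasts for the two models, the contrast correlation is about 0.94 and the critical value about 2.08. Power at 29 per cohort is 93.0-93.3% on the probability scale and 88.1-88.7% on the logit scale. The stated 90% is met on the first scale and missed by under 2 points on the second.

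**Step 2: how many subjects at 2%.**
- Partly missing: 175 × 0.02 = 3.5.
- Mean response rate: (25 + 30 + 45 + 55 + 60)/5 = 43%.
- Known failures: 3.5 × 0.57 × q = 1.2 to 1.9.
- Sum of p(1 − p) over cohorts: 0.1875 + 0.21 + 0.2475 + 0.2475 + 0.24 = 1.1325.
- Known failures drawn as responders per dataset, using cohort rates alone: 35 × 0.02 × 1.1325 × q = 0.48 to 0.75.

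**Step 3: average error.** If missingness is unrelated to outcome, true responders drawn as non-responders number 0.7 × 1.1325 = 0.79 per dataset. All true non-responders drawn as responders, visibly failing or not, also number 0.79. The errors cancel. In simulation the mean error in every cohort was within 0.03 points at 1-2%.

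If a count is missing only among known failures, all cohorts move up together: 0.09-0.12 points when 1% of known failures are affected and 0.19-0.22 points at 2%. At 2%, placebo moves by 0.19 and the active cohorts by 0.20-0.22, so differences from placebo shift by at most 0.03 points.

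**Step 4: noise.** The standard deviation of a cohort rate, √(p(1 − p)/35), is 7.3 to 8.4 points. At 2% the written rule adds an error with standard deviation 0.89 points (0.60 with the two-part fix). If that error is independent, for placebo √(7.32² + 0.89²) = 7.37, an increase of about 0.05.

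**Step 5: chance that at least 19 of 20 datasets are significant.** Paired simulations, 35 per cohort, 20 imputations, no dropout. Settings A and B take the fistula count as missing, use all seven prior HiSCR values and assume visit correlations of 0.6 and 0.8. Setting C uses one prior HiSCR with 85% agreement and q = 0.8.

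| Setting | Partly missing | Complete data | Written rule | Two-part fix | Gain (points) |
|---|---|---|---|---|---|
| A | 1% | 94.8% | 93.8% | 94.5% | 0.7 |
| B | 1% | 95.2% | 94.5% | 94.8% | 0.3 |
| C | 1% | 94.9% | 94.0% | 94.4% | 0.4 |
| A | 2% | 95.5% | 93.3% | 94.7% | 1.4 |
| B | 2% | 95.3% | 93.5% | 94.7% | 1.2 |
| C | 2% | 94.9% | 93.2% | 94.0% | 0.8 |

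A further run with only the fistula count missing gave 92.5% against 94.0% at 2%, a gain of 1.5. A simplified model found only 0.2-0.3. When the AN or abscess criterion is the missing one, the gain at 1-2% is about 0.4-0.5.

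**Step 6: add dropout.** Going from 35 to 29 is 6/35 = 17%. With 12% dropout also imputed, the gain was −0.3 to +0.9 points (simulation error about 0.5). A separate check with 10-17% dropout and 0.5-2% partial missingness gave −0.3 to +0.7 (error 0.2-0.3). In that check dropout alone lowered the chance of passing from about 94-95% to about 87-90%.

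These simulations simplify the imputation model and omit the baseline covariates.

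**The case against.** The strongest reply is that the case will hardly occur. All counts come from one examination, and section 12.1 says "computer logic checks will be run to identify items, such as inconsistent dates, missing data and questionable values". Week 16 status also decides the extension schedule (sections 3.1 and 5.4.2): non-responders start at Week 18 and responders at Week 20. A blank count should therefore surface within two weeks. Section 10.5.1 itself expects little imputation in total. This stands, and it is why only 1-2% is considered here.

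Second, any loss of power arises through the 19-of-20 rule, which penalizes all imputation, and planned dropout dominates it. This also stands.

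Third, section 10.1 leaves exact endpoint definitions to a separate SAP. That does not remove the point. The protocol already fixes the derivation, the imputation factors and even the seed, so a SAP that follows it inherits the flaw, and one that departs from it needs matching protocol text.

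A reader might infer that the rule inflates response rates in favor of IFX-1, or that it materially weakens the trial. The documents support neither. Upward bias needs missingness tied to observed failures, which nothing in the protocol indicates, and even then all cohorts move almost equally. A noticeable power loss needs partial missingness well above anything the protocol suggests.

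**Conclusion.** The point holds as a minor correction. Sections 8.2.2.2 and 10.5.1 together allow a known Week 16 non-responder to be imputed as a responder, and section 10.10 does not prevent it.

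The expected effect is very small: no bias in cohort rates if missingness is unrelated to outcome, a negligible rise in their standard deviation, and a change of roughly 0.3 to 1.5 points in the chance of passing the 19-of-20 rule without dropout. With planned dropout imputed, that change is not distinguishable from zero.

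These sizes rest on the assumed 1-2% partial missingness and on assumed relations between criteria and between visits. That the event is rare is a judgment from the trial's procedures, since the protocol gives no rate. The case for changing the text is that the rule is illogical and cheap to correct, not that it threatens the result.

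**What to change.** Adopt both parts together.

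1. **Section 8.2.2.2.** Code non-responder if any available criterion is not met; responder if all three are available and met; missing only otherwise.
2. **Sections 10.5.1 and 10.10, in matching words.** Impute the remaining partly observed subjects conditional on their observed Week 16 criteria, for example by imputing the missing count and deriving HiSCR from it. Leave the imputation of fully missing visits unchanged.

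Apply the same derivation to Week 12 HiSCR and to the prior-visit HiSCR values used as predictors.

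The first part should not be adopted alone. It turns visible failures into non-response while the remaining partly observed subjects are still imputed too low. In setting C this lowered cohort rates by 0.09-0.13 points at 1% and 0.19-0.23 at 2%. With both parts the error was at most 0.04 points.

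The cost is a few sentences and modest programming. The conditional model has few failures to fit, so it needs a small or penalized predictor set. Sample size does not change, and the text should be settled before unblinding.

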### **8.2.2.3 Hidradenitis Suppurativa-Physician's Global Assessment (HS-PGA)**

The HS-PGA is a physician-rated HS disease severity scale with a score ranging from 0 (least severe) to 5 (most severe) based on counts of abscesses, draining fistulas, inflammatory nodules, and non-inflammatory nodules measured as HS clinical parameters (Appendix [17.2](#)). The HS-PGA will be calculated based on the HS clinical parameters at each of the prespecified times when the HS clinical parameters are scheduled to be assessed during the study, as outlined in the [Schedules of Assessments](#). Lesions are counted by considering all anatomical regions.

A further efficacy endpoint is the achievement of clear or minimal severity among subjects with at least 2 grades of improvement (reduction) from Day 1 to each time point.

